2.2 Secondary Aims

Aim 1:

To explore whether: ≥ 30 day-old units will have significantly greater mean 1) phosphatidylethanolamine expression, 2) cell free hemoglobin concentration, 3) cell free heme expression, and/or 4) NTBI expression in comparison to ≤ 10 day-old units.

Aim 2:

To explore whether:

- 1) Those administered ≥ 30 day-old units will have a greater increase in the number of activated monocytes or neutrophils as defined by flow cytometry markers of activation at 2 or 24 hours post-transfusion compared to those administered ≤ 10 day units.
- 2) Those administered ≥ 30 day-old day units will have a greater increase in the concentration of NTBI, cell free hemoglobin, and free heme, compared to those administered ≤ 10 day-old units at 2 or 24 hours post transfusion.
- 3) Recipient RBC PS, PE, and microparticle expression will increase more between 2 and 24 hours after receiving ≥ 30 day-old units than after receiving ≤ 10 day units.

Aim 3:

To explore whether those administered ≥ 30 day-old units will have a more rapid increase in the concentration of HbS% and a more rapid decrease in hemoglobin over time compared to those administered ≤ 10 day-old units.

Aim 4:

To explore whether those administered ≥ 30 day-old units will have a significantly different RBC metabolomic profile 2 and 24 hours post transfusion than those provided ≤ 10 day-old units.

Aim 5:

We will address aspects of study feasibility, such as subject drop-out, rates of missing data, and the confidence intervals/precision of our recorded variables, including PS, PE, microparticles, CD62L, and the other recorded clinical variables.

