Patient Sample Processing: Blood will be obtained by port or peripheral access as available. Patient white cells will be isolated with established Ficoll separation techniques.. White cells will be tested by flow cytometry as above for key markers of activation (macrophages: CD62L, CD64, CD80, CD86, Tim1, neutrophils: The plasma fraction from each sample will be diverted to EPR (Bruker Elexys X-band system, Billerica, MA, USA), a Bio-Plex cytokine assay kit (Bio-Rad Laboratories), and a fluorescent immunoassay (DxFerr kit) to measure concentrations of free heme/hemoglobin, cytokines (IL-1, IL-6, IL-8, MCP-1), and NTBI, respectively. Clinical measurements obtained from patients will also include: CBC (4ml EDTA), reticulocyte count (4ml EDTA), HbS% (3ml EDTA), haptoglobin (1ml red top), chemistry labs (ferritin (0.5ml red top), iron saturation (1ml red top), lactate dehydrogenase (1ml red top)), urinalysis (12 ml) and blood culture (8-10ml/bottle). These clinical labs will be measured at intervals specifically defined in **Table 1**. Individual human samples of plasma and RBC will also be sent to [name] at the University of Colorado Denver to measure lipid metabolites and metabolomic profiles pre vs. post transfusion as an additional exploratory goal of this trial. The laboratory of [name] and his representatives will be receiving 30-200 individual samples of plasma and RBCs for this purpose. All samples will be de-identified.

6.3 Patient Clinical Outcomes:

A daily pain diary will be used and subjects will rate their pain on a ordinal numeric pain rating scale (0-10), indicate whether the pain was consistent with a “crisis,” indicate whether they utilized a healthcare facility, and record the amount of opioids used. Infection symptoms will also be documented daily along with the type, duration, and dose of any antibiotics taken if applicable. Subject ED and hospitalization events, and etiologies (see *definitions in 6.7*), will be recorded at regular intervals by the study coordinator during the study period using the available electronic medical record. Of note, diary completeness will be assessed at each face-to-face visit.

6.4 Patient Physical Exam:

Prior to each randomized transfusion, the PI or appropriately trained designee will perform a basic assessment of the patient. This exam will include a basic interval history (including review of any ED or hospital visits), a focused review of systems, and a focused physical exam.

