Table 1: Schedule of Measurements

Study Measure	Daily	1-4 weeks pre-transfusion	Pre-every transfusion	2hr post every transfusion	24 hr post every transfusion	2 weeks post every transfusion	End of Study
Physical exam							
AE assessment							
Med assessment			X				X
CBC w/ differential*			X		X	X	
HbS%			X		X	X	
Blood culture			X				
Urinalysis w/ reflex culture			X				
Haptoglobin			X	X	X		
Plasma Hemoglobin			X	X	X		
Basic Metabolic panel [†]			X				
Ferritin & Iron Panel [#]			X	X	X		
Lactate dehydrogenase			X	X	X		
HS-CRP			X	X	X		
RBC Unit blood donor sample			X				
Flow cytometry sample		X	X	X	X		
Study Diary	X		X			X	X

*WBC, RBC, Hgb, Hct, Plt ct

[†]Creatinine, Bicarb, Chloride, BUN, Potassium (K), Sodium (Na), Glucose, Calcium

[#]Iron, Transferrin, TIBC, % Saturation

Table 2: Lab Sample Type and Storage Conditions

Blood Samples	Sample required	Tube type	Storage	Processed By
Red cell units	6 unit segments	NA	Room temp	PI or designee
Flow	8ml	Green top	Room temp (cold after 30 minutes)	PI or designee
Flow/EPR Labs	10 ml	Cytochex	Room temp	PI or designee
Hematology Labs	10 ml	EDTA	Room temp	McLendon Labs
Chemistry Labs	5 ml	Red top	Room temp	McLendon Labs
Microbiology Blood Culture	10 ml	Culture vial	Room temp	McLendon Labs
Microbiology Urine Culture	12ml	Sterile cup	Room temp	McLendon Labs

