10.2. Analysis Plan

The analysis will be an intent to treat (ITT) with all those randomized being included in the study. For all aims, the distribution of, and relationship between, variables will be explored with summaries, plots, and tree analysis. All statistical estimates of population parameters will be tabulated along with corresponding confidence intervals (CIs). All hypothesis tests yielding large p-value (e.g., $p > \alpha$) will be reported as being inconclusive. [name], the lead biostatistician, or her designee, will perform these analyses. Where necessary for parametric assumptions, appropriate transformations will be employed with justification for their use; otherwise, non-parametric tests will be used. P-values will be reported without dichotomization wherever applicable. Data obtained from transfusion events where units of the appropriate age could not be obtained (study deviation) will be excluded from a subanalysis of the dataset, and the same distribution of, and relationship between, variables will be explored with similar summaries, plots, and tree analysis as in the ITT analysis. All subjects, regardless of age and gender, will be analyzed together as one cohort. Statistical software used in this study will be Cytel, StatXact and LogXact, SAS version 9.4, and Salford systems CART (Classification and Regression Trees). To adjust for multiple comparisons, we will use the false discovery rate approach which is less conservative than the Bonferroni approach. *Missing data:* Logistic regression will be used to investigate the possible causes for missing data and to investigate if data are missing at random (MAR). Reasons for missing data will be documented in the study database. We do not anticipate any missing data or drop-outs, but we will monitor these events. Assuming data are MAR, multiple imputations will be used for items, and for repeated measures, a random effects models will be used; the structure for the variance covariance matrix will be explored under the constraints of sample size. A sensitivity analysis will also be performed to evaluate the robustness/fragility of the study's main results to reasonable perturbations of the statistical methods and assumptions used. Results of the sensitivity analyses will only be used to guide trust in the main results.

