10.2.1 Primary Outcome Analysis

Key variables of interest:

PS – Measured as a percent of RBC positive

PE – Measured as a percent of RBC positive

Microparticles – Measured by number positive per microliter
CD62L – Measured as percent of monocytes positive
Plasma free hemoglobin – Measured as mg/dL
Non-transferrin bound iron – Measured as mg/dL
Rate of clinical infections – Measured as number per days on study

Aim 1:

The primary outcome measure is the proportion of biochemically old red cell units. Previous studies and our own work have suggested that PS, PE, and microparticles increase in a sigmoidal fashion over time.^{7,10} For this study, the cut-off for a biologically old unit would be the point at which the sigmoidal curve enters its log phase, which for PE, PS, and microparticles will be the mean value at day 21, or 8%, 3%, and 3/ μ L respectively based on these preliminary studies. This cutoff is biologically meaningful and is supported temporally by the metabolic changes that occur with red cell storage.¹¹⁹ Consequently, biochemically old units will be defined as having either a surface PE, surface PS, or a microparticle concentrations \geq the *a priori*-defined cutoff. We will compare the transfusions provided to the two groups (the proportion of biochemically old units when stored \geq 30 days compared to when stored \leq 10 days) using a Fisher exact test at an alpha of 0.05. Power: With a total sample size of 40 patients (20 in each group), we will have at least 80% power ($\alpha=0.05$) to detect a difference of at least 47% between the two randomized groups for biochemically old red cell units (close to a 100% difference is expected).

Exploratory: We will calculate the mean, minimum, and maximum levels of PS, PE, and microparticles for each study group, and we will compare the secondary outcome measures of plasma free hemoglobin, heme, and NTBI and also PS, PE, and microparticle concentrations using a two sided two sample t-test at an alpha of 0.05. We will also plan for auxiliary analyses that characterize the relationship between the PS level and the age (days) of the RBC units. This analysis will focus on estimation of the mean PS, PE, and microparticle level as a function of age (days), visualization of the data values, estimation of correlation coefficients, and evaluation of how well age (days) predicts PS, PE, and microparticle levels.

Aim 2:

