Exploratory: We will explore the relationship of blood age and transfusion of biochemically old red cell units on the change in Hb and HbS% over time, daily pain scores (0-10 as an ordinal scale), opioid use and dose, ED and hospitalization rate, infection symptoms, new alloantibody formation, and antibiotic use during the 3-month study period. We will compare groups using a Fisher exact test. We will also plan for auxiliary analyses of the outcome variables in which the explanatory variable is the age (days) of the RBC units --to characterize the degree to which age (days) can accurately predict the clinical and physiologic outcome measures defined.

AIM 4:

We will calculate the mean, median, minimum, and maximum levels of each metabolic compound analyzed by [name] in his laboratory at the University of Colorado. Analysis tools and methods will be determined by his research team, and will focus on changes in the patient and the unit pre and post transfusion.

AIM 5:

Feasibility Analysis: We will assess important variables necessary to develop a future larger clinical trial on this subject. Areas that we will investigate during the course of this trial will include frequency and content of missing data, subject drop out rates, and estimates of outcome measure precision. For this study, we will evaluate the number of males, females, and adolescents that enroll in the study to inform future studies. We do not expect there to be differences in the key outcomes based on these variables, and plan to analyze all 40 subjects together as one cohort, but differences by age and gender will be evaluated and considered.

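### Section 10.2.1 names Fisher's exact test for non-binary Aim 3 outcomes, gives patient-level power for a unit-level test in Aim 1, and does not say how Aim 2 uses up to three transfusions per patient

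*Combined protocol and SAP*

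**What the plan says.** **Aim 3, exploratory (section 10.2.1).** The plan will explore the relation of blood age and biochemically old units "on the change in Hb and HbS% over time, daily pain scores (0-10 as an ordinal scale), opioid use and dose", followed by ED and hospital use, infection symptoms, new alloantibodies and antibiotic use. The group comparison is then given in one sentence: "We will compare groups using a Fisher exact test". No cut-points are given. Secondary Aim 3 (section 2.2) asks whether the older-unit arm shows "a more rapid increase in the concentration of HbS% and a more rapid decrease in hemoglobin over time". Table 1 schedules CBC and HbS% before, 24 hours after and "2 weeks post every transfusion". Section 6.3 has patients "rate their pain on a ordinal numeric pain rating scale (0-10" every day.

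**Aim 1 (section 10.2.1).** The outcome is the proportion of biochemically old units. The comparison is worded as "We will compare the transfusions provided to the two groups", and test and power follow directly: "using a Fisher exact test at an alpha of 0.05. Power: With a total sample size of 40 patients (20 in each group", with at least 80% power for a 47-point difference. Every unit at the three study transfusions is sampled (section 6.1).

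**Aim 2 (section 10.2.1).** The outcome is the change in CD62L MFI from before transfusion to 2 hours after, compared by a two-sample t-test on the log scale, with 80% power for a ratio of 1.35. Section 2.1 ties that power to 40 patients. The 2-hour sample is taken after each study transfusion (section 6.2).

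**General text (section 10.2).** Non-parametric tests are the fallback where parametric assumptions fail. Within the missing-data text, "for repeated measures, a random effects models will be used". A subanalysis leaves out transfusion events for which units of the assigned age could not be found.

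**The concern.** The three gaps share a cause: the named test does not match the structure of the data.

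- **Aim 3.** Rate of change, ordinal scores repeated daily and dose are not binary. Fisher's test needs a cut-point for Hb, HbS% and dose, and that cut-point could be chosen after the data are seen.
- **Aim 1.** Several units go to one patient. A Fisher test on pooled units treats them as independent, and the quoted power belongs to a different analysis.
- **Aim 2.** First transfusion, mean of three and a model over all three are all compatible with the text, so the choice could be made late. The pre-transfusion value enters only through subtraction, which is not its most efficient use.

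Section 2.1 calls this a feasibility study whose data will feed the calculations for a larger trial, and Aim 5 assesses precision. An analysis at the wrong level gives misleading precision for that purpose.

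**Working it through.** **Aim 1: reproducing the 47 points.** Inputs from section 10.2.1: 20 patients per group, Fisher exact, alpha 0.05 (two-sided assumed). No base rate is stated, so it is varied. Exact power for a 47-point difference, one yes/no value per patient:

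| Lower rate | 0.05 | 0.10 | 0.20 | 0.25 | 0.30 | 0.40 |
|---|---|---|---|---|---|---|
| Power | 0.917 | 0.870 | 0.795 | 0.774 | 0.780 | 0.847 |

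The plan's figure is therefore a patient-level one, correct to within about 3 points (minimum 77.3%, at 26.5% vs 73.5%). The Aim 3 infection outcome, which is one value per patient, carries the same 47%.

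**Aim 1: Fisher on pooled units.** The Preliminary Studies section gives 896/407 = 2.20 units per encounter, so 3 x 2.20 = 6.6 per patient if that applies here. The design effect is 1 + (6.6 - 1) x ICC = 1.56 at ICC 0.1 and 2.12 at 0.2. Simulated type I error (beta-binomial, 20 patients per arm, 6 units each, 20,000 trials):

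| Assumed ICC | 0 | 0.05 | 0.1 | 0.2 |
|---|---|---|---|---|
| Type I error, true rate 50% or 95% | 2-3% | 4-6% | 5-9% | 10-14% |

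With 7 units per patient the upper ends at ICC 0.1 and 0.2 are about 10% and 16%. A Wilcoxon test on each patient's proportion of old units holds 4-5%. It has 80% power for about 20, 22, 28 and 34 points at ICC 0, 0.05, 0.2 and 0.5 (rates symmetric about 50%).

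**Aim 3: cost of a cut-point.** Assume one normal summary value per patient, 20 per arm. The t-test has 80% power at a difference of 0.909 SD; Wilcoxon has 78%. Fisher after a split has:
- 0.466 with the cut midway between the arms;
- 0.468 with the cut at the control median;
- 0.475 with the cut at the control upper quartile;
- 0.518 with the cut at the pooled median (simulated).

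Fisher needs about 1.25-1.4 SD for 80%.

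**Aim 3: how time must enter.** Three time points x three transfusions give up to 9 Hb and HbS% values per patient. Hb and HbS% reset at each transfusion. Assume 28-day cycles and an arm difference that grows 0.02 per day from the latest transfusion. On days 0, 1, 14, 28, 29, 42, 56, 57 and 70 the difference is 0, 0.02, 0.28, 0.56, 0.02, 0.28, 0.56, 0.02 and 0.28. A straight line through these has slope 0.0034, and 0.0034/0.02 = 17%. One arm-by-time term across the whole study would miss most of the effect.

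**Aim 2: implied variability.** SD of the log ratio = ln(1.35)/0.909 = 0.300/0.909 = 0.330 if the power refers to one change per patient. The documents give no SD, so this cannot be checked.

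**Aim 2: baseline adjustment at one transfusion.** With equal pre and post variances and correlation r, the change-score variance is 2s²(1 - r) and the adjusted variance is s²(1 - r²). The ratio is (1 + r)/2 = 0.75 at r = 0.5 and 0.85 at r = 0.7, a cut of 25% and 15%. The detectable ratio falls from 1.35 to 1.30 and 1.32. Power at a true ratio of 1.25 rises from 55% to 67% and 62%.

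**Aim 2: first transfusion or patient mean, both unadjusted.** The variance of the mean of three is (1 + 2ρ)/3 times that of one change, where ρ is the within-patient correlation of changes (assumed). With equal effects at all three, power at 1.25 is 95%, 91%, 81% and 64% at ρ = 0, 0.1, 0.3 and 0.7, against 55% for the first transfusion alone. If later effects are a fraction f of the first, the mean loses only when f < (3 x sqrt((1 + 2ρ)/3) - 1)/2 = 0.37, 0.45, 0.60 and 0.84 at those values of ρ.

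**The case against.** The best defence is section 10.2, which already offers non-parametric tests, confidence intervals for all estimates and random-effects models for repeated measures. That shows the right tools are acceptable to the sponsor. It does not close the gap: the wording is generic, the random-effects clause sits in the missing-data text, and 10.2.1 names different tests outcome by outcome.

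Other points stand in part:

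- The Aim 3 list is exploratory. Fisher suits its binary items, and an r x c version would need no cut-point for 0-10 pain. It would still ignore the order of the scores and the repetition over days.
- In Aim 1 the harm is small. Unit age properties are measured before the unit reaches the patient, so the ICC may be low, and at 0 the test is conservative. At 47 points, pooled Fisher has at least 99% power in simulation (20 patients per arm, 6 units each, ICC 0-0.7), partly helped by its inflated type I error.
- In Aim 2 a change-score t-test is valid under randomisation; adjustment is a gain in efficiency.

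Two stronger readings are tempting. A reader might infer that the first study transfusion must be primary, because inventory is checked only before that one (section 4.2). The documents do not support this: the section 10.2 subanalysis removes individual off-age events, which implies that later events are in the dataset, and the patient mean has more power unless later effects are clearly smaller. A reader might also infer that Aim 2 treats repeated events as independent. No passage says so, and the 40-patient power statement points the other way.

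**Conclusion.** The point holds on all three aims as a mismatch between named test and data structure. It should be corrected but does not threaten the trial.

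- **Aim 3** has the clearest mismatch. Fisher cannot answer the rate-of-change question, and a split costs about 28-33 points of power (80% to 47-52%) for one normal summary value per patient.
- **Aim 1** states a power that is sound for one binary value per patient (77-80% at lower rates 0.2-0.3, higher below that) but does not describe a unit-level test. Type I inflation rests on an assumed ICC and about 6 units per patient. It would be wrong to infer that the Aim 1 conclusion is in danger: a difference near 100% would be found either way.
- **Aim 2** leaves the use of up to three transfusions open. The size of the gain from adjustment rests on an assumed pre/post correlation of 0.5-0.7 and is worked out for a single transfusion only.

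**What to change.** **Aim 3, exploratory.**
- For Hb and HbS%, use a linear mixed model with time counted from the most recent transfusion (restarting each cycle), transfusion number, arm, arm-by-time within cycle and a random patient effect. The sample before transfusion 2 or 3 then belongs to the end of the preceding cycle.
- For daily pain use a mixed or ordinal model, and for opioid dose a mixed model. Refer explicitly to the random-effects clause of section 10.2.
- Keep Fisher for binary items such as new alloantibody or any antibiotic use, each with a written yes/no definition.

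**Aim 1.** Compare each patient's proportion of biochemically old units by a permutation or Wilcoxon test, and restate the power for that test.

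**Aim 2.** Fix one analysis in advance, with one value per patient or a random patient effect, adjusted for log CD62L MFI from just before the first study transfusion. The patient mean over study transfusions, or an equivalent mixed model, fits both the 40-patient power and the event-level subanalysis. Report the first transfusion as a sensitivity analysis. Confirm MFI as the scale, since the variable list in 10.2.1 gives CD62L as a percentage and section 2.1 as a number of cells. Because sections 6.6 and 8.6 give the statistician the assignments, date the choice before CD62L data are examined by arm.

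**Cost.** Plan wording and a little more programming; no new visits or samples. The patient mean gives up power only if effects at later transfusions are clearly smaller than at the first.

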The primary outcome measure is the change in CD62L (activated) circulating monocyte/macrophage MFI at 2 hours post-transfusion compared to the subject pre-transfusion. We will compare the two groups (\geq 30 day-old compared to \leq 10 day-old unit exposure) using a two sample two-sided t-test of the log at an alpha of 0.05. Power: We will have at least 80% power to detect a change in the ratio of 1.35 post-transfusion if the variability is similar to that seen in our preliminary data.

Exploratory: We will use a general(ized) linear model to include biochemically old units transfused (Aim 1 outcome), regardless of unit age, as a covariate in our analysis. Other co-variates in this model will include free heme, cell free hemoglobin, and NTBI. We will similarly compare other obtained activation measures as outcomes: activation markers for monocytes, neutrophils (as listed in section 6) and measured plasma cytokine

concentrations (section 6). We will also plan for auxiliary analyses of the outcome variables in which the explanatory variable is the age (days) of the RBC units --to characterize the degree to which age (days) can accurately predict the clinical and physiologic outcome measures defined. Lastly, as an exploratory aim, we will evaluate the *in vivo* change in recipient red cell PE/PS positivity at 2 and 24 hours post transfusion.

Aim 3:

The primary outcome variable is the rate of post-transfusion infections in the patient. The primary estimand is the treatment effect defined as the difference between the regimen-specific proportions of patients in the target populations that would experience post-transfusion infections. This population parameter will be estimated as a function of the proportions observed in the sample of patients studied. The point estimate will be reported along with the corresponding 95% confidence interval estimate. The presence of an indwelling catheter will be used as a key co-variate in this analysis. *Power:* A difference of 20% will be of clinical interest. We do not expect to have adequate power for this pilot study but at an alpha of 0.05 with 20 subjects in each group we will be able to detect a difference of 47% between the proportions.

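### Fisher's exact test for the exploratory yes/no outcomes of Aim 3 is valid but conservative; naming Boschloo's test in advance would cost almost nothing and could add some power

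*Combined protocol and SAP*

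**What the plan says.** Section 10.2.1, Aim 3 (Exploratory), lists a mixed set of outcomes: change in Hb and HbS%, daily pain scores, opioid use and dose, ED and hospitalization rate, infection symptoms, new alloantibodies and antibiotic use. It then names one test for all of them: "We will compare groups using a Fisher exact test". It gives no alpha, sidedness, event rate or power for these comparisons.

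The surrounding plan sets the scale. Aim 1 is tested "using a Fisher exact test at an alpha of 0.05", and its power statement reads "With a total sample size of 40 patients (20 in each group"). The Aim 2 test is a "two sample two-sided t-test of the log at an alpha of 0.05", which is the basis for reading Fisher's test as two-sided here. The Aim 3 primary outcome is not assigned Fisher's test: it is a difference in proportions with a 95% confidence interval and indwelling catheter as a covariate.

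Section 10.2 adds a false discovery rate adjustment and lists the software: "Statistical software used in this study will be Cytel, StatXact and LogXact, SAS version 9.4". The documents do not discuss the conservatism of Fisher's test or any unconditional alternative.

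**The concern.** The design fixes the arm sizes but not the total number of patients with an event. Fisher's test conditions on that total. With few patients, only a handful of p-values are then attainable, and the true type I error falls well below the nominal level.

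An unconditional exact test that still respects 5% can use more of the allowance. In a small study that concedes inadequate power for clinical outcomes, and that will report large p-values as inconclusive, the choice of test could leave some real differences unrecognised without any gain in validity that the plan asks for.

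**Working it through.** **Inputs.** From the plan: 20 per arm, alpha 0.05. Assumed: a two-sided test, and event rates, which the documents do not give and which are therefore scanned.

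**1. The plan's own figure.** Section 10.2.1 claims "we will have at least 80% power" for a 47-point difference. Take the least favourable (centred) rates, 26.5% v 73.5%, with mean 50%:
- Uncorrected: n = [1.96·√(2·0.5·0.5) + 0.842·√(0.265·0.735 + 0.735·0.265)]² / 0.47² = (1.386 + 0.525)² / 0.2209 = 16.5, so 17 per arm.
- Continuity-corrected: n′ = (16.5/4)·[1 + √(1 + 4/(16.5·0.47))]² = 20.6, so 21 per arm, against 20 stated.
- Exact two-sided Fisher power at these rates is 77.3%, and 80% needs 48.3 points.

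The 47 points therefore reproduce as a rounded figure at about 20 per arm. They are stated for Aim 1 and the Aim 3 primary outcome, not for the exploratory outcomes.

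**2. True type I error at 20 v 20.** Write b(x; n, π) for the binomial probability. For a rejection set R,

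size(π) = Σ over (x, y) in R of b(x; 20, π)·b(y; 20, π),

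and power is the same sum with p₁ and p₂ in place of π. All 21 × 21 = 441 tables were enumerated.
- Fisher (p ≤ 0.05): 214 tables; maximum size 2.53%, at a common rate of about 34% or 66%. Size is 1.2% at a rate of 10% and 0.2% at 5%.
- Boschloo: reject when Fisher's two-sided p is at or below the largest cutoff that keeps the maximum size within 5%. That cutoff is 0.0915; 234 tables; maximum size 4.64%.

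Because 0.0915 exceeds 0.05, the Boschloo set contains the whole Fisher set, so its power cannot be lower.

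**3. One table by hand.** For 2/20 v 8/20 there are 10 events among 40 patients. Fisher's two-sided p = 2·[C(20,0)C(20,10) + C(20,1)C(20,9) + C(20,2)C(20,8)] / C(40,10) = 2·(184,756 + 3,359,200 + 23,934,300) / 847,660,528 = 0.065. Boschloo's p, the largest size over π of the set with Fisher p ≤ 0.065, is 0.039. A different two-sided definition, as in one common software routine, gives 0.035 for the same table.

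**4. Power at 20 v 20** (gains from unrounded values).

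| Assumed rates | Fisher | Boschloo | Gain, points |
|---|---|---|---|
| 10% v 30% | 24.2% | 33.9% | 9.7 |
| 20% v 40% | 19.2% | 26.5% | 7.3 |
| 10% v 40% | 49.2% | 60.9% | 11.7 |
| 20% v 50% | 40.9% | 49.2% | 8.3 |
| 30% v 70% | 59.9% | 70.5% | 10.6 |
| 26.5% v 73.5% | 77.3% | 85.2% | 7.9 |
| 5% v 15% | 7.0% | 8.8% | 1.8 |
| 2% v 15% | 12.0% | 13.2% | 1.3 |

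With both rates between 5% and 95%, the gain is 5.7 to 9.7 points at a 20-point difference, 8.1 to 11.7 at 30 points, 6.9 to 10.6 at 40 points and 3.8 to 7.9 at 47 points. It is at most 2.0 at 60 points and nil at 90.

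**5. Slightly unequal arms.** The synopsis randomizes in blocks of 5, which cannot split evenly between two arms, so 20 v 20 is not assured; one missing outcome gives 20 v 19.
- 19 v 21: Fisher's maximum size is 3.4%. Depending on which arm has the higher rate, the gain is about 0 or 4 points for 10% v 30%, 3 or 3.5 for 20% v 40%, 1 or 5 for 10% v 40%, and 7 or 5 for 20% v 50%. For 30% v 70% it is still about 10.
- 20 v 19: Fisher's maximum size is 3.6%. The gain is under 1 point for the first three of these, at most 2.6 for 20% v 50%, and 3.9 for 30% v 70%.

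**The case against.** Fisher's test controls the type I error, the plan does not contradict itself, and choosing between two valid exact tests is partly a matter of preference. The outcomes are exploratory. Section 10.2 intends to report p-values without dichotomization and estimates with confidence intervals, so an exploratory p of 0.065 rather than 0.039 triggers no decision. The false discovery rate adjustment may put the working threshold below 0.05 for either test, which the power figures above ignore. All of this stands, and it makes the change optional.

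The reach is also limited. Of the listed outcomes only new alloantibody formation is plainly binary. Others are rates, scores or doses, and become yes/no only if the analyst reduces them to, say, any antibiotic use. If alloantibodies are uncommon over three months, the gain at 20 v 20 is 1 or 2 points.

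A reader might infer that every binary comparison in the trial loses some 8 to 12 points of power. The documents do not support that: they state no event rates, and the gain depends on the rates, the size of the difference and the exact split between arms.

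A reader might also extend the point to Aim 1. But that comparison is worded at the level of transfused units, so an enumeration of 20 v 20 patients does not describe it. The plan also says "close to a 100% difference is expected", where the gain is nil.

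**Conclusion.** The point holds as an optional improvement. For exploratory Aim 3 outcomes analysed as yes/no per patient, the two-sided Fisher test uses at most about half of its nominal 5% at exactly 20 v 20, and about 3.4% to 3.6% at 19 v 21 or 20 v 19. Boschloo's test keeps the error at or below 5% and never has less power. Its gain is about 6 to 12 points at 20 v 20 for differences of 20 to 40 points with rates between 5% and 95%. It is little for rare events, and it can shrink to almost nothing with slightly unequal arms.

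These figures assume a two-sided test, an unadjusted 5% threshold and event rates that are not in the documents. It would be wrong to read this as an invalid test or as a remedy for low power: at 20% v 40%, power is still only about 27% after the change.

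**What to change.** In the Aim 3 exploratory paragraph of section 10.2.1, state before unblinding that outcomes analysed as yes/no per patient will be compared with Boschloo's two-sided unconditional exact test, with a matching unconditional exact confidence interval for the difference and Fisher's p-value shown beside it. List the outcomes to which this applies.

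Define the two-sided version, because implementations differ (0.039 and 0.035 in the worked table). Name only one unconditional test: for rare events they can diverge, and at 2% v 15% a Barnard-type test gains 13.4 points where Boschloo's gains 1.3, so a choice made after seeing the data would not be neutral.

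Leave the Aim 1 test unchanged on this ground. The cost is a sentence or two in the analysis plan and slightly more computation, with no extra data. The listed software already includes packages for exact inference, but the statistician should confirm that the available version offers the chosen test and interval.
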